Study Title: Double-Blinded Randomized Control Trial Comparing Liposomal Bupivacaine and Plain Bupivacaine in Transversus Abdominis Plane For Deep Inferior Epigastric Artery Perforator (DIEP) Flap Breast Reconstruction

NCT # 03700970

Document date: October 1, 2018

Statistical Analysis

Patient characteristics were summarized as appropriate, using mean (standard deviation [SD]) and median (25th-75th interquartile range [IQR]) for quantitative variables and counts (percentages) for qualitative variables. Unadjusted comparisons of patients between the plain bupivacaine group and the liposomal bupivacaine group were performed using Wilcoxon test or Pearson chi-square test. The effect of the study intervention on daily oral opioid intake in oral morphine equivalents (OME) was examined using linear mixed effects regression model, adjusting for post-operative day (as a categorical variable), intervention status (plain bupivacaine/ liposomal bupivacaine), and their interaction. Since there were repeated measurements of OME for 7 post-operative days, a random intercept indexed by subject number was used in the linear mixed effects regression model. All analyses were performed using the R Programming Language 3.3.0 (R Foundation for Statistical Computing, Vienna, Austria). P<0.05 was considered a statistically significant difference.

Sample size calculations were based on demonstrating superiority of the TAP block with liposomal bupivacaine. A simulation-based power analysis was used to evaluate statistical power under the following assumptions: 1) use of linear mixed effects regression after log transformation of the opioid intake outcome, 2) average opioid consumption on days 0, 1, 2, and

3 is 30, 90, 70 mg mEq under standard of care, 3) use of liposomal bupivacaine will result in a 20% reduction in opioid consumption at each study day, and 4) the between- and within-subjects coefficients of variation are 20% and 60%, respectively (these values are based on standard of care data from our institution). Thus, the minimum-detectable difference is a 20% reduction in average opioid consumption at each study day. Under these assumptions, 60 participants are needed to achieve 80% power.

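### The SAP does not say which test of the mixed model is primary, or on which scale opioid use is analysed; fitted raw, its day-specific standard errors would be wrong

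*SAP*

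**What the plan says.** The analysis part of the SAP (Statistical Analysis, first paragraph) states that "daily oral opioid intake in oral morphine equivalents (OME) was examined using linear mixed effects regression model". The fixed effects are given as "adjusting for post-operative day (as a categorical variable), intervention status (plain bupivacaine/ liposomal bupivacaine), and their interaction", and the covariance as "a random intercept indexed by subject number was used in the linear mixed effects regression model". No transformation, no variance that differs by day and no rule for zero-opioid days is stated. The significance rule is "P<0.05 was considered a statistically significant difference", attached to no particular coefficient or contrast and without sidedness.

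The sample size paragraph of the SAP lists "use of linear mixed effects regression after log transformation of the opioid intake outcome" as its first assumption. It names days 0 to 3, gives control means in the words "3 is 30, 90, 70 mg mEq under standard of care" (three values; the leading 3 is the last day number), and concludes that "the minimum-detectable difference is a 20% reduction in average opioid consumption at each study day". The between-patient CV is 20% and the within-patient CV 60%; the result is 60 participants for 80% power.

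The number of days also differs. The SAP writes "Since there were repeated measurements of OME for 7 post-operative days", while the primary aim in the protocol (Rationale and Specific Aims) runs from day 0 to day 7, which is eight days. The protocol's Statistical Considerations section names no model, scale or contrast, so it does not fill the gap.

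**The concern.** Two choices are left open.

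- **Contrast.** With an arm-by-day interaction in the model, no single p-value is the arm effect. Under R's default coding the arm coefficient is the effect on the reference day only. The day average, the interaction test, a joint test and the separate day contrasts answer different questions and have very different power.
- **Scale.** An analyst who follows the model sentence literally would fit raw OME. With constant CVs, the raw standard deviation rises and falls with the day mean, but the model as written has one residual variance. A constant 20% reduction is also not constant in mg: on the listed means it is 6, 18 and 14 mg, so it appears as an arm-by-day interaction. On the log scale it is one number.

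At stake are the validity of any day-specific result, the match between the analysis and its power basis, and the freedom to choose test and scale after the data are seen.

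**Working it through.** **Inputs.** From the SAP sample size paragraph: means 30, 90, 70 mg (taken in order as days 0, 1, 2), ratio 0.8, CVs 20% and 60%, 60 patients. Equal allocation, 30 per arm, follows from the protocol's blocks of 2 or 4. Assumptions: no dropout; two-sided 0.05 unless stated; lognormal data unless stated. The log variances are ln(1.04) = 0.0392 between and ln(1.36) = 0.3075 within patients; the effect is ln(0.8) = −0.223.

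**1. The SAP's own figure, on the log scale.** With balanced data the day-averaged arm effect over k days is a two-sample comparison of patient means, with SE = √[(2/30)(0.0392 + 0.3075/k)] and 58 degrees of freedom. Day means do not enter.

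| Days averaged | SE | Effect/SE | Power, two-sided |
|---|---|---|---|
| 1 | 0.152 | 1.47 | 30% (31% with a normal reference) |
| 3 | 0.0972 | 2.30 | 62% |
| 4 | 0.0880 | 2.54 | 70% |
| 6 | 0.0777 | 2.87 | 81% |
| 7 | 0.0745 | 3.00 | 84% |
| 8 | 0.0720 | 3.10 | 86% |

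At one-sided 0.05, four days give 81%. The stated 80% can therefore be reached, but only under some combinations of contrast, window and sidedness, and the SAP does not say which was used. The interaction test has about 5% power on this scale, simply because the assumed ratio is the same every day.

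**2. Day-specific standard errors on the raw scale.** The raw SD on a day is mean × √(1.04 × 1.36 − 1) = 0.644 × mean. With 30 per arm and no effect, the true SEs are 0.644 × √(2/30) × (30, 90, 70) = 5.0, 15.0 and 11.6 mg. A model with one intercept variance and one residual variance gives every day the same SE, based on the root mean square of the day means: √[(900 + 8100 + 4900)/3] = 68.1 mg, so 11.3 mg.

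- Model SE divided by true SE is 68.1/30 = 2.27, 68.1/90 = 0.76 and 68.1/70 = 0.97.
- Type I error, 2[1 − Φ(1.96 × ratio)], is below 0.1%, 14% and 6%.
- Simulation with 20,000 trials gives average ratios of about 2.2, 0.75 and 0.96, and type I error of 0%, 14% and 6%.
- Gamma data with the same CVs give the same pattern of ratios, so this does not hinge on lognormality. On the log scale the SEs are right on every day.

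**3. Day-averaged test on the raw scale.** Simulated type I error is about 5%, raw and log. For power over the three listed means, the variance of a patient's mean is 0.04 × 63.3² + 1.04 × 0.36 × 13,900/9 = 739 mg² under control and 0.64 × 739 = 473 mg² under treatment. The SE is √[(739 + 473)/30] = 6.36 mg, the effect is 0.2 × 63.3 = 12.7 mg, and effect/SE is 1.99. Simulated power is 51%, against 62% on the log scale.

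**4. How far that comparison depends on assumptions.** For eight days, three assumed sets of later means were used: days 3 to 7 at 50, 40, 30, 20, 15 mg; at 60, 50, 45, 40, 35 mg; and all at 70 mg.

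| Setting | Raw | Log |
|---|---|---|
| Lognormal, three days, no zeros | 51% | 62% |
| Lognormal, eight days, no zeros | 76–81% | 86% |
| Gamma, three days | 50% | 50% |
| Gamma, eight days | 76–81% | 79% |
| Lognormal, eight days, 10% zeros on days 4–7 | about 77% (74–77%) | log(OME + 1) about 55% (51–62%); log(OME + 10) about 75% (71–78%) |

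The zero frequency is an assumption, independent of arm and patient; ranges are over the three sets of means. The documents give neither a zero frequency nor a distribution.

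**The case against.** **Log was plainly meant.** A reader may reasonably infer this from the power paragraph. But log appears only as a power assumption, and a log fit cannot use a zero-opioid day without a rule. The protocol itself expects that a block may remove the need for narcotics, and the window runs past discharge, so such days are foreseeable.

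**The raw analysis is legitimate.** This stands for the day-averaged test. Its type I error is 5%, and with complete data it is total mg divided by the number of days, which is close to the protocol's aim of comparing the amount used. The 14% error rate belongs to day-specific tests, which the SAP never calls primary. A reader might infer that the trial's main result would be a false positive 14% of the time; the documents do not support that.

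**A raw fit must lose power, so log OME should be primary.** A reader might infer this as well. It holds for lognormal data without zeros, but the two scales are about equal for gamma data, and the ranking can reverse when zero days occur. If zeros were more frequent in the liposomal arm, log could regain power. The documents do not settle which scale is better.

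**Only the seven- or eight-day window reaches 80%.** This would be too strong: six days two-sided, or four days at one-sided 0.05, also give 81%, and the SAP states no sidedness.

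**Conclusion.** The point holds as a gap in specification with a measurable consequence. The primary test, its window, its sidedness and the analysis scale are not stated, and the model sentence does not match the log-scale power basis. Depending on which test is taken as primary, log-scale power with 60 patients runs from about 31% for one day to 86% for the eight-day average (two-sided 0.05, CVs as stated, no dropout).

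If OME is fitted raw with one residual variance, day-specific standard errors are wrong in both directions. That result rests only on the SAP's means and constant CVs. The raw-versus-log power comparison for the day average rests on distribution, later-day means and zero frequency, none of which the documents give, so no general power loss is claimed. This should be fixed before the data are analysed; it does not invalidate the mixed model itself.

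**What to change.** 1. **Name one primary test:** the one-degree-of-freedom arm effect averaged with equal weights over one stated window. State its sidedness, reconcile the SAP's seven days with the protocol's days 0 to 7, and make the interaction and day-specific effects secondary.
2. **State one scale and make the power statement match it.** Either use log OME, with a zero-day rule fixed in advance and checked by simulation at a plausible zero frequency, or use raw OME with power restated for the raw day-averaged contrast. Keep the other scale as a sensitivity analysis.
3. **If any day-specific result is reported in mg,** allow a separate residual variance for each day.

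The cost is a few sentences in the SAP and a few lines of R, with no new data. The stated power may become slightly less favourable. On the log scale the result is a ratio whose value depends on the zero rule: even without zeros, on the listed means, a true 20% reduction is estimated as 19.5% with c = 1 and 16.1% with c = 10. Equal weighting of daily ratios also differs from a ratio of total mg unless the effect is the same every day.

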Local analgesia, in the form of transversus abdominis plane (TAP) block that is administered in the operating room prior to the incision under ultrasound guidance, has been advocated to provide improved analgesia in the perioperative and postoperative periods. This is a promising approach that can decrease or even eliminate the need for narcotics in the postoperative period. This is a standard procedure at VUMC, and part of the Enhanced Recovery Pathway, for patients undergoing abdominally-based free flap breast reconstruction. However, there is debate regarding the best local anesthetic for these purposes. Liposomal bupivacaine has been used widely and is believed to provide adequate analgesia for more than 48 hours after surgery. On the other hand, plain bupivacaine is significantly cheaper and has also been shown to have promising and lasting analgesic results. To date, there are not randomized trials comparing the two local analgesics in a well-defined group of plastic surgery patients in general and also specifically in patients undergoing abdominally-based free flap breast reconstruction.

Rationale and Specific Aims

This study is designed to compare the efficiency of TAP blocks using liposomal bupivacaine versus plain bupivacaine that is administered in the operating room under ultrasound guidance prior to the incision in patients undergoing abdominally-based free flap breast reconstruction.

The ***primary aim*** of the study will be to compare the amount of supplemental postoperative narcotic analgesia (both intravenous and oral) required by the study groups in oral morphine equivalents from postoperative days 0 to 7. The amount of postoperative analgesia will be documented daily until postoperative day 7. It will be obtained from the medical records during hospitalization, and with daily phone calls after the patients get discharged with instructions to document this data daily.

The *secondary aims* will be:

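### The SAP's 80% power at 60 participants assumes that no patient ever has an opioid-free day, so it is unsupported for daily opioid intake counted to postoperative day 7

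*SAP*

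**What the plan says.** The sample size paragraph of the SAP (Statistical Analysis) derives 60 participants and 80% power by simulation. Its first assumption is "use of linear mixed effects regression after log transformation of the opioid intake outcome". The others are:

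- control averages for the early days, where the list of four days ends "3 is 30, 90, 70 mg mEq under standard of care" (as the text reads, three values for four named days);
- "use of liposomal bupivacaine will result in a 20% reduction in opioid consumption at each study day";
- "the between- and within-subjects coefficients of variation are 20% and 60%, respectively".

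No mean is given for days 4 to 7, and no frequency of zero days for any day.

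The analysis paragraph of the same section reads differently: "The effect of the study intervention on daily oral opioid intake in oral morphine equivalents (OME) was examined using linear mixed effects regression model". It mentions no transformation. The terms of that model are given as "adjusting for post-operative day (as a categorical variable), intervention status (plain bupivacaine/ liposomal bupivacaine), and their interaction", and each patient has a random intercept.

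In the protocol (Rationale and Specific Aims), the primary aim covers days 0 to 7: "The amount of postoperative analgesia will be documented daily until postoperative day 7". The data come from hospital records and, after discharge, from daily telephone calls. Of TAP blocks in general, the Background says: "This is a promising approach that can decrease or even eliminate the need for narcotics in the postoperative period". Neither document says how a day without opioids is handled.

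**The concern.** Zero has no logarithm. A model on the log scale with the stated coefficients of variation (CVs) produces only positive intakes, so the power simulation cannot have represented opioid-free days. Such days are most plausible late in the window, which is where the SAP gives no inputs at all.

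Two things are at stake. First, the 80% is the only justification for 60 participants, and it may not describe the trial that will be analysed. Second, the power paragraph and the analysis paragraph use different scales. If that is settled by adopting the log model, someone must then choose what to do with zeros. Dropping zero patient-days removes any benefit that shows up as opioid-free days. Adding a constant lets the constant set the size of the estimate. With no rule written down, that choice could be made after the data are seen.

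**Working it through.** **1. Inputs from the documents.** N = 60, taken as 30 per arm because the permuted blocks are balanced. Effect: ln(0.8) = -0.223. CVs of 20% and 60% give log-scale SDs of √ln(1.04) = 0.198 and √ln(1.36) = 0.555, or 0.20 and 0.60 if the CVs are used directly as log SDs. Significance level 0.05, sidedness not stated.

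**2. Reproducing the stated figure, with no zeros.** For a patient's mean log intake over m days, SD = √(s_b² + s_w²/m), and n per arm = 2(1.96 + 0.842)² SD² / 0.223².

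- m = 7, log SDs 0.20 and 0.60: SD = √(0.04 + 0.36/7) = 0.302. Then n = 29 per arm, N = 58, and power at 60 is 81.5%.
- It also reproduces with exact lognormal SDs at m = 6 (N = 58, 81.9%), or at m = 4 one-sided (N = 58, 81.4%).
- It does not reproduce two-sided on the early days alone. Exact lognormal SDs give 63% at m = 3 and 72% at m = 4.

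So 80% is attainable, but only from a model in which every patient takes opioids on every day counted.

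**3. Adding zero days that rise over the week.** Assumptions not in the documents: POD 3-7 control means of 50, 35, 25, 18 and 12 mg; zero-day probability rising linearly from 0 at POD 0 to 30% or 70% at POD 7 (15% or 35% of all patient-days), equal in both arms; patient-level propensity SD 1.2 on the logit scale. On other days intake falls by 20%. Exact lognormal SDs, eight days, 30 per arm, two-sided test on patient-level summaries. For complete data, the unlogged test corresponds to one overall arm contrast in the random-intercept model.

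| Handling | No zeros | 30% by POD 7 | 70% by POD 7 |
|---|---|---|---|
| log(OME); zero days dropped where they occur | 86-87% | 81% | 72% |
| log(OME+1) | 86-87% | 22% | 11% |
| Unlogged OME | about 75% | 61% | 44% |
| Ratio of mean OME | about 75% | 61% | 45% |

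Other assumed shapes of the rise moved these figures by up to about 12 points without changing the pattern. The ratio of means estimated 0.80 throughout, with type I error of 5%.

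**4. A flat zero rate.** Seven days, log SDs 0.20 and 0.60, assumed control means 30, 90, 70, 70, 60, 50 and 40 mg, same zero rate on every day and in both arms, 20% reduction otherwise:

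| Zero days | log(OME+0.1) | log(OME+1) | log(OME+10) | Zeros dropped | Unlogged |
|---|---|---|---|---|---|
| 0% | 81% | 81% | 80% | 81% | 72% |
| 5% | 29% | 47% | 66% | 80% | 68% |
| 10% | 17% | 32% | 55% | 78% | 64% |
| 30% | 8% | 13% | 28% | 70% | 46% |

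**5. Benefit only as opioid-free days.** In the flat setting with zeros on 10% v 25% of days and amounts otherwise unchanged:

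- Dropping zeros shows an effect of about 0%, with a 2% chance of a favourable significant result.
- Constants of 0.1, 1 and 10 show reductions of 60%, 44% and 23%, with power of 98%, 96% and 86%.
- Unlogged OME has 42% power.

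In the rising setting, with an odds ratio of 2.5 for a zero day, a test of mean OME has about 24% power (19-31% across the zero patterns) and log(OME+1) about 53-61%.

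**The case against.** The strongest reply is that the log appears only among the power assumptions. The analysis paragraph models OME with no transformation, and there a zero day simply enters as zero. That is correct. A reader might infer that the SAP plans to drop zero days or add a constant; it states neither. Those consequences follow only if the log model is adopted to bring the two paragraphs into line.

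A reader might also infer that the protocol expects opioid-free days, or that the patients who benefit most would be lost. The Background sentence describes a possibility for TAP blocks generally, which both arms receive, and gives no rate. A mixed model on logged data would lose zero patient-days; it would lose a patient only if every day were zero.

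Three further points stand. Dropping zeros costs little power when only amounts fall (81-72% above), so 80% does not collapse under every rule. A constant can raise power when the benefit is itself more opioid-free days, so the trouble there is an estimate that depends on the constant. And every figure with zeros rests on assumed rates; if zeros are very rare, the constant hardly matters.

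None of this rescues the 80%. On the unlogged scale the SAP states, power is about 72-75% with no zeros under the assumed means, and lower with them.

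**Conclusion.** The concern holds as a gap in the power justification. The 80% at 60 participants comes from a log-scale model without zero days and with early-day means only, while the outcome runs to POD 7 and includes time at home. If zero-day rates rise to 30-70% by POD 7, power is about 61-44% for the stated unlogged scale and about 22-11% for log(OME+1). These ranges depend on assumed later-day means and zero-day rates, because the documents give neither.

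The documents do not support the stronger conclusion that the primary result will be blind to opioid elimination or set by an arbitrary constant. That would follow only if the log were carried into the analysis without a sound rule for zeros. This should be fixed together with the mismatch between the logged power model and the unlogged analysis model.

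**What to change.** 1. State in the SAP that the primary analysis does not log-transform OME and that zero days are kept as zeros.
2. Name one primary estimate, the reduction in mean OME over POD 0-7. Either a log-link model for mean OME clustered on patient, or the stated unlogged mixed model with a single overall arm contrast, would do. The contrast needs naming because the model includes a day-by-arm interaction: a joint test of arm plus interaction would have only about 41-57% power at 60 on the log scale without zeros.
3. Rerun the power simulation at 60 under that model, using the institution's own POD 0-7 means and zero-day rates. The SAP already draws its CVs from institutional data.

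The drafting cost is a few sentences and one simulation. The real cost is the number. Power becomes about 75% instead of 86-87% for the log model when there are no zeros, and lower when there are, which may reopen the sample size. The log-link option shows no power gain over unlogged OME. If fitted by unweighted GEE, it also needs stronger missing-data assumptions than a mixed model, which matters for intake collected by telephone. Either choice is weak (about 24%) if the benefit is only more opioid-free days, and the SAP should say so.

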Patients eligible for the study will be seen by the participating attendings at Vanderbilt University Medical Center, or one of their associates. The patient will be told about the study and given an opportunity to read the consent. If they wish to participate, they will be asked to sign the consent.

Participants will be randomized to receive liposomal bupivacaine or plain bupivacaine in a permuted block fashion, in block of sizes 2 or 4. For each block, block size will be selected uniformly at random. This method of randomization ensures balance between groups following every second or fourth allocation. The patients will be randomized after providing written informed consent in the outpatient clinic. Following randomization, the plastic surgeons performing the surgery and assessments will be blinded to study treatment arm. Patients will also be blinded to the study treatment arm. The anesthesia team and some of the ancillary research staff will not be blinded to study treatment arm.

Study Procedures

Patients randomly assigned to the liposomal bupivacaine group or plain bupivacaine group will receive this intervention intra-operatively prior to the initiation of surgery.

Local analgesia (TAP blocks) will be administered under ultrasound guidance in the operating room after the patient is intubated and under general anesthesia. Transfascial injections will be performed by the anesthesiologist using an epidural needle. Under sterile conditions and ultrasound guidance, the fascial plane between the internal oblique and transversus abdominis muscles (muscles of the abdominal wall) will be identified at the anterior axillary line, midway between the costal margin and iliac crest. The epidural needle will be inserted through the skin to the appropriate fascial plane, and the local anesthetic will be injected in that plane. Then the needle will be removed and discarded, and the patient will be prepped and draped to start the surgery.

Liposomal bupivacaine group: 20mL of Exparel® 1.3% mixed with 20mL of 0.25% bupivacaine, for a total of 40mL of local anesthetic mixture, 20mL to be injected on each side.

Regular bupivacaine group: 20mL of 0.25% bupivacaine injected on each side.

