Local anesthetic toxicity or nerve injury will be considered serious adverse events. Also allergic reactions to the local anesthetic will be considered adverse events. These patients will be withdrawn from the study and appropriate treatment will be instituted. The anesthesia care team will identify such an event and report it.

Statistical Considerations

Sample size calculations were based on demonstrating superiority of the TAP block with liposomal bupivacaine.

The sample size calculation for the oral morphine equivalent requirements was based on one of our previous studies on Enhanced Recovery Pathway for free flap breast reconstruction. Calculations showed that randomizing 60 patients will obtain 80% power to detect a difference between the two groups.

Privacy/Confidentiality Issues

Collected data will be stored in a password protected REDCap™ database with sole access delineated by the investigators and study personnel of the study.

Follow up and Record Retention

The data will be extracted from the EMR via of EPIC (eStar) and entered in a RedCap™ database. Paper copies of the surveys will be kept in a locked cabinet by the investigators of the study until study completion of all data analysis and then subsequently securely destroyed.

Collected data will include demographics, amount of supplemental postoperative narcotic analgesia both intravenous and oral, visual analog pain scale, time to return of bowel function, time to first opiate use, incidence of narcotic complications, and Quality of Life. Some of these variables will be collected at several times points as described above.

Records will be retained for 6 years following the study completion.

References

Practice guidelines for acute pain management in the perioperative setting. A report by the American Society of Anesthesiologists Task Force on Pain Management, Acute Pain Section. *Anesthesiology*. 1995; 82(4):1071-81.

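### The SAP's 20% minimum-detectable difference on each study day matches no named test: a single day has about 31% power for 20%, and no across-day contrast is defined

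*SAP*

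**What the plan says.** The sample size paragraph of the SAP (Statistical Analysis, second paragraph) describes a simulation using a mixed model on log-transformed opioid intake. It assumes that liposomal bupivacaine lowers intake by 20% on every study day and that "the between- and within-subjects coefficients of variation are 20% and 60%, respectively". From this it concludes that "the minimum-detectable difference is a 20% reduction in average opioid consumption at each study day", and then that "Under these assumptions, 60 participants are needed to achieve 80% power".

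The analysis paragraph of the SAP specifies a linear mixed model for daily oral morphine equivalents with a random intercept per patient, "adjusting for post-operative day (as a categorical variable), intervention status (plain bupivacaine/ liposomal bupivacaine), and their interaction". It names no contrast that averages or sums the arm effect over days. The significance rule is general: "P<0.05 was considered a statistically significant difference". Sidedness is not stated; the calculation is framed as superiority.

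The Protocol (Statistical Considerations) says only that "randomizing 60 patients will obtain 80% power to detect a difference between the two groups". Its primary aim (Rationale and Specific Aims) compares opioid use over postoperative days 0 to 7 and singles out no day.

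**The concern.** A simulation that puts the same 20% effect on several days shows what the trial can detect when those days are combined. It does not show what can be detected on one day. The SAP moves from the first to a sentence that reads like the second. The planned model makes this matter: with categorical day and an arm-by-day interaction, the arm effect is specific to a day unless an averaged contrast is defined, and none is.

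If day-by-day results are reported, a reader told that 20% is detectable each day could take a non-significant day as evidence against a 20% saving. A mix of significant and non-significant days could look like an effect limited to certain days, although a constant 20% effect would be expected to produce that pattern.

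**Working it through.** **Inputs.** From the SAP: 60 participants, a 20% reduction, CVs of 20% and 60%, the log scale, alpha 0.05. From the Protocol (Enrollment/Randomization): permuted blocks of 2 or 4, of which it says "This method of randomization ensures balance between groups following every second or fourth allocation", so 30 per arm. My assumptions: two-sided test, lognormal CVs, no missing data. The random-intercept covariance is the SAP's own.

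**Log-scale quantities.**
- Effect: −ln(0.80) = 0.2231
- Between-subject variance: ln(1 + 0.20²) = 0.0392
- Within-subject variance: ln(1 + 0.60²) = 0.3075

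**Reproducing the SAP's 80%.** For an arm contrast averaged over k days, SE = √[2 × (0.0392 + 0.3075/k)/30] and power = Φ(0.2231/SE − 1.96).

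| Days averaged | Two-sided power | Total N for 80% |
|---|---|---|
| 3 | 63% | 90 |
| 4 | 72% | 74 |
| 6 | 82% | 58 |
| 7 | 85% | 54 |
| 8 | 87% | 50 |

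Four days tested one-sided give 81% (N = 58). Seven days two-sided, with the CVs used directly as log-scale SDs, give 81.5% (N = 58). The stated pair of 60 and 80% can therefore be reached, but only for an effect averaged over days. Simulation of the balanced random-intercept model agrees (70% for 4 days, 84% for 7).

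**A single day (k = 1).**
- Variance: 0.0392 + 0.3075 = 0.3467
- SE of the log ratio: √(2 × 0.3467/30) = 0.152
- Power for 20%: 0.2231/0.152 = 1.468; Φ(1.468 − 1.96) = 31%. One-sided, Φ(1.468 − 1.645) = 43%
- Reduction detectable with 80% power: 1 − exp(−2.80 × 0.152) = 34.7%
- Smallest observed reduction with p<0.05: 1 − exp(−1.96 × 0.152) = 25.8%
- 95% CI for an observed 20% reduction: exp(−0.2231 ± 0.298) = 0.59 to 1.08, that is, from a 41% reduction to an 8% increase
- Patients for 80% power at 20%: 2 × 0.3467 × (2.80/0.2231)² ≈ 109 per arm, about 220 in total after rounding up

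The simulated mixed-model day contrast has 31% power for a 20% reduction and 80% power for a 35% reduction.

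**Other conventions for the single day.**

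| Convention | Power for 20% | Detectable at 80% power |
|---|---|---|
| Lognormal CVs, two-sided | 31% | 34.7% |
| Lognormal CVs, one-sided | 43% | 31.5% |
| CVs used as log SDs, two-sided | 28% | 36.7% |
| Raw scale, two-sided | 27% | 38.5% |

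**Joint test.** The interaction model also allows one test of arm and arm-by-day terms together. With k degrees of freedom and noncentrality 15k × 0.2231²/(0.0392k + 0.3075), its power under a constant 20% effect is 46% for 3 days, 50% for 4, 56% for 7 and 57% for 8.

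**Pattern over days.** With a true 20% reduction on each of 4 days, simulation gives 4 × 0.31 ≈ 1.2 significant days on average, all four significant in about 2% of trials, and none in about 27%.

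**The case against.** The best defence is that the sentence repeats the wording of the SAP's third assumption and is followed by a reference back to those assumptions. Read in sequence, it may only describe the simulated alternative, a constant 20% ratio on every day, and not a separately powered test per day. That reading is fair and may be what was meant. It does not settle the matter, because the SAP defines no contrast that would test such a common effect.

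A reader might go further and infer that the SAP has miscalculated, that 60 patients are too few, or that non-significant days will be misread. The documents do not support these. Some across-day readings do reach 80% with 60 patients. No day-by-day tests are listed, there is no rule for interpreting a non-significant day, and default software output from such a model would be a reference-day effect with differences from it. Misreading is a risk if day-specific results are shown, not a certainty. The 2% figure is likewise only illustrative, since no planned decision requires every day to be significant.

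It is also fair to object that a correction should not simply declare the trial powered for a pooled effect. On the most direct reading, four days and two-sided, the power is 72%.

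**Conclusion.** The sentence needs correcting under either reading. As a per-day claim it fails on the SAP's own inputs: about 31% power for 20% (27% to 43%) and about 35% detectable with 80% power (31.5% to 38.5%). No convention tried brings a single day to 80% power for a 20% reduction. As a common-effect claim it has no named test. The fault lies in the minimum-detectable-difference sentence and the missing contrast, not necessarily in the sample size.

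The central figures assume two-sided 5%, lognormal CVs, 30 per arm, the random-intercept covariance and no missing data. The single-day result does not depend on how many days were simulated, so it is unaffected by the sample size paragraph naming four days but giving three means.

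**What to change.** 1. Name one day-averaged arm contrast from the mixed model as the primary test, on the log scale used in the power analysis, and state its days and sidedness. The SAP analyses 7 days, while the Protocol's days 0 to 7 are 8.
2. Replace the minimum-detectable-difference sentence with: *A 20% reduction is the common effect assumed on all study days and applies to the day-averaged contrast. Assuming a two-sided 5% level, lognormal CVs of 20% and 60%, 30 patients per arm and no missing data, any single day has about 31% power for a 20% reduction and 80% power for a reduction of about 35%.*
3. Restate the power of the day-averaged contrast for the days actually used, instead of asserting 80%. Two-sided, it is about 72% for 4 days, 85% for 7 and 87% for 8.
4. Report day-specific ratios with 95% CIs as descriptive, and state that a non-significant day does not exclude a 20% reduction.

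This is more than rewording: it fixes the primary contrast in advance and settles the analysis scale, since the SAP mentions the log transformation only under the power assumptions. The stated sensitivity becomes less favourable. No patients or data are added.
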